4.4 Patient Withdrawals

A patient (and in this case the parents or guardian) may withdraw from the trial at any time. This is expected to be a very infrequent occurrence in this trial in view of the testing procedure's similarity to routine clinical practice. If the parents or guardian indicate that they want to withdraw the child from the study, the investigator personally should attempt to speak with them to determine the reason. If a plano group patient with high hypermetropia is intolerant to atropine and the plano lens, it is preferred that the patient wear his/her enrollment glasses and continue on atropine rather than withdraw from the study. The decision to restart the enrollment glasses should be discussed with a protocol chair.

Patients who receive alternate treatment, e.g. patching, for at least one week, will be dropped from the study after completion of the main outcome exam (8C).

4.5 Risks

There are no risks involved in this study that would not be part of usual care.

4.6 Risks of Examination Procedures

The procedures in this study are part of daily pediatric eye care practice in the United States and pose no known risks. As part of a routine usual-care exam, the patient may receive cycloplegic/dilating eye drops.

4.7 Adverse Events/Risks

The risks involved in the study are identical to those that would be present for a patient treated with the study treatment regimens who is not participating in the study.

593
594
595
596
597
598
599
600
601
602
603
604
605
606
607
608
609
610
611
612
613
614
615
616
617
618
619
620
621
622
623
624
625
626
627
628
629
630
631
632
633
634
635
636
637
638
639
640
641
642

4.7.1 Side Effects of Treatment

1. Local side effects of minimal severity include allergic lid reactions, local irritation, conjunctival hyperemia, and follicular conjunctivitis. Potential systemic side effects include dry skin and mouth, tachycardia, fever, flushing and irritability. These effects occur very uncommonly in the dosage schedule (one drop a day) suggested in this protocol as noted in the previous studies of atropine treatment. Simons and coworkers⁸ found the risk of allergic reactions to be less than 1%. Additional safety data can be derived from the literature describing the chronic topical atropine treatment for the attempted prevention of myopia. In the study by Brodstein and colleagues,¹² 253 patients were treated for an average of 33 months with daily atropine 1% drops. Neither local nor systemic side effects of any significance were noted. This therapy lasted 5 times as long and involved twice as much drug as in the proposed protocol. In ATS1,¹ among 204 patients, an ocular side effect was reported at least once for 26% of patients, most commonly light sensitivity (18%), lid or conjunctival irritation (4%), and eye pain or headache (2%). Facial flushing was reported for two patients, one of whom remained on atropine with no further problems and one of whom was switched to homatropine. Atropine was not discontinued because of side effects in any other patients. No other systemic side effects of atropine were reported. In ATS4 ocular side effects, most commonly light sensitivity, were reported by 13 (16%) patients in the daily group and 25 (29%) patients in the weekend group.² However, these symptoms did not lead to a change in treatment. Facial flushing and fever were reported for 2 patients in the daily group, one of whom remained on atropine and the other was switched to homatropine.
2. Atropine produces dilation of the pupil, which can increase the light that enters the eye. Although it has not been demonstrated that atropine used for several months will have harmful ocular effects, excessive exposure to light theoretically could be toxic to the retina. Atropine has been used long-term to prevent the progression of myopia without an apparent adverse effect on acuity.¹²⁻¹⁵ To minimize risk from pupil dilation, sunglasses (or flip-ups) will be provided for patients who do not require glasses. Hats with brims or visors will be encouraged.
3. When a patient develops adverse effects serious enough to discontinue atropine, the investigator should call a Protocol Chair to discuss the case. If atropine is discontinued, then the patient should be switched to homatropine 5%. Such a change in the treatment regimen will be recorded on a follow-up examination form. Homatropine, if needed, will be sent directly to the patient from the Jaeb Center.

4.7.2 Reverse Amblyopia

Atropine could decrease the visual acuity in the sound eye, although this is almost always reversible. In ATS1, as noted in section 1.2, results were inconclusive as to whether atropine produced a transient decrease in sound eye acuity. However, the results did not indicate that treatment caused a permanent reduction in sound eye acuity. After two years of follow up, there was no difference in sound eye acuity comparing the two treatment groups. As noted in section 1.2, there is uncertainty as to whether the use of a plano lens increases the risk of reverse amblyopia compared to atropine alone. One of the objectives of the study is to determine this.

The diagnosis and management of reverse amblyopia at the interim visits is left to the investigator's judgment. At visit 8C a protocol for testing the sound eye with reduced vision should be followed (see section 3.2.3).

643
644 **4.7.3 Development of Strabismus**
645 The study treatment could precipitate the development of a manifest ocular deviation. If treatment
646 precipitates the development of an ocular deviation (e.g., esotropia), the parent will be advised to
647 have the patient see the investigator as soon as possible. If the deviation is confirmed on
648 examination, the decision as to whether to continue or discontinue therapy will be left to the
649 investigator's and parent's decision. If amblyopia treatment is to be discontinued during the
650 treatment period of the study, a Protocol Chair should be called to discuss the case. The
651 development of a new heterotropia is an accepted risk of amblyopia therapy as part of standard care.
652 Such an event occurred with both patching and atropine therapy with atropine in about 18% of cases
653 in ATS1. About 13% of patients had resolution of their preexisting strabismus with treatment. In
654 ATS4, 2 of 168 patients developed a new esotropia >8 D, while 5 patients had resolution of a small
655 angle esotropia. This risk in this study is no greater than it would be with standard care of
656 amblyopia.

657
658 In view of the short duration of the study, it is preferred that strabismus surgery be deferred until the
659 patient completes the study; however, such surgery is allowed at the discretion of the clinician if
660 medically indicated. Performance of strabismus surgery will be reported in the comment section of
661 the Follow-up Exam Form.

662 663 664 **4.8 Reporting of Adverse Events**

665 Each investigator is responsible for informing his/her IRB of serious treatment-related adverse
666 events and for abiding by any other reporting requirements specific to his or her IRB.

667 Data on the complications of the study treatments will be tabulated regularly by the Coordinating
668 Center for review by the Steering Committee. Serious complications will be reported expeditiously
669 to the Data and Safety Monitoring Committee, which will receive a full adverse event report semi-
670 annually. Following each DSMC data review, a summary will be provided to IRBs.

671 672 **4.9 Patient Payments**

673 The parent/guardian of each patient will be compensated \$25 per visit for completion of the 5-week,
674 10-week, and 18-week visits. For patients remaining in follow up after the 18-week visit, \$25 will
675 be paid for each 8-week interval visit, up to a maximum of \$75 (maximum of \$150 for the entire
676 study). If there are extenuating circumstances, additional funds may be provided for travel if
677 expenses exceed \$25 and the patient will be unable to complete the visit without the reimbursement
678 of the travel expenses.

679 680 **4.10 Discontinuation of Study**

681 The study may be discontinued by the Steering Committee (with approval of the Data and Safety
682 Monitoring Committee) prior to the preplanned completion of enrollment and follow-up for all
683 patients.

684 685 **4.11 Contacts by the Jaeb Center for Health Research**

686 The Jaeb Center serves as the PEDIG Coordinating Center. The Jaeb Center will be provided with
687 the parent/guardian's contact information. The Jaeb Center will maintain direct contact with the
688 parents or guardian of each patient. Permission for such contacts will be included in the Informed
689 Consent Form. The principal purpose of the contacts will be to develop and maintain rapport with
690 the family and to help coordinate scheduling of the outcome examination. One phone contact is
691 planned for each patient in the first month after enrollment. Additional phone contacts will be made

692 if necessary to facilitate the scheduling of the patient for follow-up visits. A patient newsletter,
693 study updates, and a study logo item may be sent. Patients will be provided with a summary of the
694 study results in a newsletter format after completion of the study by all patients.
695

Chapter 5: Sample Size Estimation and Statistical Analysis

696
697
698 The estimation of sample size and statistical analysis plan are summarized below and detailed in
699 separate documents.

701 **5.1 Sample Size Estimation**

702 The primary analysis will include only patients with moderate amblyopia (visual acuity of 20/40 to
703 20/100); therefore the sample size was estimated in order to have the needed power for analysis of
704 these patients. Based on data from previous studies (ATS1 and ATS4), we assumed a standard
705 deviation for the 18-week outcome score of 0.16 logMAR and a correlation between baseline and
706 18-week week outcome score of 0.40. We decided to use a two-sided alpha of 0.05, with 90%
707 power to detect a 0.075 logMAR difference between treatment groups in the mean improvement in
708 acuity from baseline. With these assumptions, and accounting for 5% loss to follow up, we have
709 selected a necessary sample size of 172 patients with moderate amblyopia.

710
711 During the time period of recruitment of patients with moderate amblyopia, patients with severe
712 amblyopia (visual acuity 20/125 to 20/400) will be enrolled without a limit or formal sample
713 size/power estimation. Based on enrollment in our previous studies, it is predicted that ¼ of
714 recruited patients with amblyopia in the range of 20/40 to 20/400 will have severe amblyopia. Thus,
715 during recruitment of the 172 patients with moderate amblyopia, it is expected that 58 patients will
716 be recruited with severe amblyopia.

717 718 **5.2 Primary Analysis for Efficacy**

719 All primary analyses will include the cohort of patients with moderate amblyopia (20/40 to 20/100).
720 The primary analysis will be a treatment group comparison of logMAR visual acuity scores in the
721 amblyopic eye obtained 18 weeks after randomization, adjusted for baseline acuity scores in an
722 analysis of covariance (ANCOVA) model.

723
724 As a secondary analysis, acuity at 18 weeks will be categorized as $\geq 20/25$ vs $< 20/25$. Patients who
725 receive alternate treatment, e.g. patching, for at least one week, will be categorized in the group
726 which did not reach the better visual acuity. The outcomes in each group will be analyzed by a
727 Fisher's exact test for association with treatment group.

728
729 To explore whether there is a difference in the initial effect of treatment, the visual acuity data from
730 the 5-week and 10-week visits will be used to compare the treatment groups in an analysis of
731 covariance similar to that described for the primary analysis. To explore differences in rate of
732 improvement, a repeated measures regression analysis will be performed.

733
734 The effect of fixation preference at 5 weeks on the primary outcome (logMAR acuity in amblyopic
735 eye at 18 weeks) without respect to treatment group will be evaluated in an ANCOVA model,
736 adjusting for baseline acuity score. Additionally, the possibility of interaction between fixation
737 preference and treatment group will be evaluated in an ANCOVA model.

738
739 The treatment effect in subgroups based on baseline factors will be assessed in preplanned
740 secondary analyses. The subgroups of most interest will be those based on baseline amblyopic eye
741 visual acuity ($\geq 20/50$, $< 20/50$), cause of amblyopia, age, and prior treatment.

742

743 **5.3 Primary Safety Analysis**

744 The primary safety analysis will be a treatment group comparison of logMAR sound eye visual
745 acuity score obtained 18 weeks after randomization (after atropine has been discontinued for at least
746 two weeks), adjusted for baseline acuity scores in an analysis of covariance (ANCOVA) model.

747
748 A second analysis will compare the proportion of subjects with a 3 or more line decrease from
749 baseline to 18 weeks in sound eye acuity with a Fisher's exact test.

750

751

752 **5.4 Severe Amblyopia**

753 In an exploratory analysis, data from patients with severe amblyopia (20/125-20/400) will be
754 evaluated in a treatment group comparison of logMAR visual acuity scores obtained 18 weeks after
755 randomization, adjusted for baseline acuity scores in an analysis of covariance (ANCOVA) model.
756 The primary safety analysis will be repeated as well.

757

758 **5.5 Interim Analyses**

759 No formal interim efficacy analyses of the outcome data are planned in view of the timing of its
760 collection as it seems unlikely that there would be sufficient data and reason to terminate the trial
761 early. However, an efficacy and safety report will be provided to the DSMC twice a year. DSMC
762 reports also will include tabulations of local and systemic adverse effects of atropine. Nevertheless,
763 a minimal amount of alpha spending (0.001) will be allocated for each DSMC review of the data.

764 There are projected to be two DSMC data reviews prior to the end of the trial. The final alpha level

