3.1 Treatment Groups

406 Each patient is randomly assigned to one of the two treatment groups:

- 407 • Atropine 1% once each weekend day in the sound eye
- 408 • Atropine 1% once each weekend day in the sound eye plus a plano lens for the sound eye

409

410 For both treatment groups:

- 411 • Atropine is discontinued after 16 weeks (2 weeks prior to visit 8C).
- 412 • If acuity in amblyopic eye becomes the same or better than acuity in the sound eye, the
- 413 frequency of atropine should be maintained through 16 weeks.
- 414 • If reverse amblyopia is suspected or strabismus develops or worsens, treatment is at
- 415 investigator discretion.
- 416 • If an allergy to atropine develops, the patient can be switched to homatropine 5% after
- 417 discussion with a Protocol Chair.

418

419 Notes

- 420 1. The study will be providing atropine drops and sunglasses (or flip-ups) for the patients. The
- 421 dispensing of atropine will be recorded on the ATS Atropine Accountability Log.
- 422 2. Wearing a hat with a brim for outdoor activities is to be encouraged.
- 423 3. Morning is the preferred time for administration of the atropine. However, if there is an
- 424 overriding reason why the parent/guardian wants to administer the atropine at night, this will be
- 425 acceptable.
- 426 4. If a patient is noncompliant with treatment, the parents should be encouraged to persist with the
- 427 treatment to the best of their ability.
- 428 5. Deviations from the treatment protocols or prescribing non-protocol treatment should be
- 429 discussed with a Protocol Chair prior to initiating.
- 430 6. Discontinuation of therapy due to reverse amblyopia, strabismus, or atropine allergy should be
- 431 discussed with a Protocol Chair.
- 432
- 433 7. Both treatment groups will receive atropine in the sound eye, which should help tolerance of
- 434 wear of the full or near-full cycloplegic correction. Therefore, bilateral atropine to relax
- 435 accommodation for two days is not likely necessary, and will not be allowed.

436

437 **3.1.1 Compliance**

438 A calendar log will be maintained by patients on treatment. The preprinted calendar will contain

439 customized instructions about treatment.

- 440 1. An adhesive sticker will be placed by the child on the log on days when the atropine was used.
- 441 2. These logs will be turned in to the investigator at each of the protocol visits. At each visit, the

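### Section 5.3 compares sound-eye harm between arms only at 18 weeks, so reverse amblyopia found at an interim visit, acted on and recovered by then is not counted

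*Protocol*

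**What the plan says.** Protocol section 5.3 names two sound-eye analyses. The primary one is an ANCOVA of the sound-eye "acuity score obtained 18 weeks after randomization (after atropine has been discontinued for at least" two weeks). The other is categorical: "A second analysis will compare the proportion of subjects with a 3 or more line decrease from" "baseline to 18 weeks in sound eye acuity with a" Fisher's exact test. The synopsis (1.5) likewise reports sound-eye data at the 18-week visit only. The 5- and 10-week analyses are in 5.2, under efficacy, and follow the form of the primary amblyopic-eye analysis.

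On events before 18 weeks, section 3.1 states: "If reverse amblyopia is suspected or strabismus develops or worsens, treatment is at" the investigator's discretion. Section 4.7.2 agrees: "The diagnosis and management of reverse amblyopia at the interim visits is left to the" investigator's judgment. The same section describes sound-eye loss on atropine as nearly always reversible.

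On the question to be answered, section 1.3 wants to know whether the plano lens with atropine harms the sound eye and, if so, how often. Section 4.7.2 notes uncertainty about whether the lens raises the risk of reverse amblyopia and adds: "One of the objectives of the study is to determine this".

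Sound-eye acuity is measured at visits 8A, 8B and 8C (3.2), and a Follow-up Examination Form is completed for every examination.

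**The concern.** The harm in question can appear, be noticed, lead to a change of treatment and resolve, all before the only visit at which section 5.3 looks for it. What 5.3 measures then depends partly on how sites respond to the harm: the more reliably they detect and act on sound-eye loss, the lower the measured rate.

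If the plano lens has no added effect on the sound eye, the frequency of harm may be understated in both arms but the comparison is not tilted. If the lens does cause more loss, more plano-arm children would be changed early and leave the count, and the arm difference shrinks. The trial could then report no excess of reverse amblyopia when there had been a transient one, which is part of what 1.3 and 4.7.2 set out to learn.

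**Working it through.** **1. Can an event leave the count?**

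- Detection: the sound eye is tested at weeks 5 and 10 (3.2).
- Action: treatment may be changed on suspicion (3.1, 4.7.2).
- Recovery: loss is expected to reverse (4.7.2), and 4.3 refers to recovery after treatment is stopped or reversed.
- Time available: 18 − 5 = 13 weeks, or 18 − 10 = 8 weeks, before 8C.
- Scoring: 5.3 takes the 18-week acuity, with no rule for a child whose treatment was changed because of the sound eye.

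Such a child is a non-event in the Fisher test and contributes a recovered score to the ANCOVA.

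**2. The plan's own figure.** The protocol gives no power for the sound-eye comparison. Its sample size is for efficacy, and it reproduces:

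- Residual SD = 0.16 × √(1 − 0.40²) = 0.1466.
- n per arm ≈ 2 × (1.960 + 1.282)² × 0.1466² / 0.075² ≈ 80.3, so 81, or 162 in total.
- 162 / 0.95 = 170.5, so 171, against the stated 172.

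This point does not challenge that number. It supplies the evaluable count used below: 172 × 0.95 / 2 ≈ 82 per arm, assuming equal allocation.

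**3. Illustration of the dilution.** The only by-arm rates in the protocol are from ATS1 (1.2), for loss of two or more lines at 6 months: 7/43 = 16.3% with the plano lens added and 4/123 = 3.3% with atropine alone. Fisher's test on these counts gives p = 0.007 (the protocol reports P=0.01). Assume those were the rates of all on-study loss and that the same share r recovers in each arm before 8C. Visible rates are then 16.3% × (1 − r) and 3.3% × (1 − r). Exact two-sided Fisher power at 0.05, 82 per arm:

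| r (assumed) | Expected visible events, plano vs alone | Difference (points) | Power |
|---|---|---|---|
| 0 | 13.3 vs 2.7 | 13.0 | 78% |
| 0.25 | 10.0 vs 2.0 | 9.8 | 59% |
| 0.50 | 6.7 vs 1.3 | 6.5 | 34% |
| 0.75 | 3.3 vs 0.7 | 3.3 | 7% |

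Using 0.048, the final level in 5.5, changes each power by less than 0.01. With equal r, hidden cases fall about five to one in the plano arm (16.3 / 3.3), only because the assumed rates do.

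The table shows the direction and how steep the loss can be. It does not give the power of the 5.3 test, for the reasons under the objection.

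**The case against.** **The 18-week time point is deliberate.** Section 1.2 attributes the low rate of sound-eye loss in ATS4 partly to testing at least two weeks off drops and retesting apparent losses. Visit 8C has a masked examiner, retest, refraction and recheck rules. The protocol specifies none of these for 8A and 8B, where the sound eye is tested on atropine in trial frames. This stands. A reader might infer that 18 weeks is the wrong time point; the documents do not support that. It measures persistent loss well and should stay.

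**The ATS1 rates do not fit the 5.3 event.** They are two-line losses, whereas 5.3 counts three or more lines, so rates would be lower. They come from a single 6-month visit, so they are already net of loss that had resolved. The lens was given to children who had improved too little on daily atropine. In ATS4, which used no plano lens, the weekend arm had 1 loss in 85. All of this stands, so the powers are illustrative only.

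**An excess in the plano arm is not established.** A reader might infer that the hidden cases will fall mainly there. Section 4.7.2 calls the added risk uncertain, so the bias toward zero is conditional on a true excess.

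**Counting interim events has costs.** A change for suspected reverse amblyopia is an unmasked, undefined judgment by someone who knows which child has the plano lens, and could itself create an arm difference. Counting any of three visits also admits false positives: with the rounded rates of 16% and 3%, an assumed 5 extra points per arm (21% vs 8%) lowers power from 79% to 59%. This is why the interim count should not replace the 18-week event.

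**Section 5.2 does not make 5.3 inconsistent.** For the 20/25 endpoint, children who "receive alternate treatment, e.g. patching, for at least one week, will be categorized in the group" that missed the better acuity. That shows the protocol can carry a treatment change into an outcome, but the rule covers one secondary efficacy analysis and the primary ANCOVA has none. A reader might see a contradiction; there is not one.

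**The children are not invisible.** Discontinuation for reverse amblyopia is to be discussed with a Protocol Chair (3.1), complications are tabulated (4.8), and the DSMC receives safety reports twice a year (5.5). Section 5 also defers detail to separate documents. These are fair points, but tabulation for monitoring is not a stated between-arm analysis, and the two comparisons that 5.3 does fix do not answer how often harm occurs.

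**Conclusion.** The point holds in a limited form. The 18-week analyses are sound for persistent loss but do not count reverse amblyopia that was detected, acted on and recovered before 8C, so they can understate how often the sound eye is harmed. If the plano lens truly causes more loss, they also understate the difference between arms.

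The size cannot be fixed from the protocol. The share of events recovered by 18 weeks is not given, nor is any rate at the three-line threshold. The fall from 78% to 34% rests on borrowed two-line rates, 82 children per arm and an assumed recovery of half in each arm. The table should not be read as a forecast, nor the point as showing that the lens is harmful or that the planned safety analyses are invalid.

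**What to change.** Leave the 18-week ANCOVA and the 18-week Fisher test in 5.3 as they are. Add a supplementary comparison by arm of the proportion of children with either:

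1. a sound-eye loss of the size used in 5.3 (three or more lines from baseline) at 8A, 8B or 8C; or
2. randomized treatment stopped or changed before 8C for suspected reverse amblyopia, whatever the 18-week acuity.

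Report the two components separately and combined, beside the 18-week result. State that the comparison is supportive, because interim readings are taken on atropine with no masked examiner or retest specified, and component 2 is unmasked investigator judgment. If the separate analysis plan already contains such a comparison, a reference to it in 5.3 is enough.

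The cost is a few lines of analysis text and a recorded reason for any treatment change, if the Follow-up Examination Form (not shown) does not already capture one. No visit or test is added, and how children are managed does not change.
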